This open label investigation further evaluates the safety, efficacy and potential mechanisms of action of a new form of electroconvulsive therapy (ECT). Both the efficacy and adverse cognitive effects of ECT are highly contingent on the intracerebral current paths and current density of the ECT stimulus (1993, [name] et al., 2000b, [name], 2004a, McCall et al., 2000, [name] et al., 2008). However, the impedance of the skull and individual differences in skull anatomy severely limit the spatial targeting of stimulation, and create marked individual differences in intracerebral current density (Weaver et al., 1976, [name] et al., 1994, Deng et al., 2009, Peterchev et al., 2010). To address these problems, we have been exploring various means of overcoming this limitation. One approach is to induce the seizure using magnetic fields [magnetic seizure therapy (MST)] ([name], 1994b, Lisanby et al., 2001b, Lisanby et al., 2003a, Lisanby et al., 2001c, Luber et al., 2013, Kayser et al., 2013, Hoy et al., 2013, Fitzgerald et al., 2013). MST uses high power repetitive magnetic stimulation to induce sufficient current flow in brain to elicit self-sustaining seizures. MST must overcome technological barriers as the energy transfer from current in a coil to that induced in brain is inefficient, and it is not clear that a form of MST will be developed that is sufficiently powerful to match the efficacy of ECT.

An alternate approach is to modify the electrical stimulus to induce focal seizures. The most common methods of ECT administration in the US use a bidirectional, constant current, brief or ultrabrief pulse, with large (approximately 3 sq. in. surface area) and identically sized and shaped electrodes. In contrast, in this protocol we have coupled unidirectional current flow with an electrode geometry involving a small and large electrode that differ by more than 5:1 in surface area.

Unidirectional currents were widely used in ECT during the 1940's and 1950's and continue to be used in European and American devices today (Alexander, 1955, Epstein and Wender, 1956, Friedman, 1949, Friedman, 1942, Hovorka et al., 1960, Impastato et al., 1951, Pacella, 1952, Rappa and Tanowitz, 1959). Indeed, a unidirectional current option is incorporated in the US marketed Thymatron System IV (Somatics Corp.). Transcranial electrical stimulation can be made focal by

stimulating with an anode-cathode arrangement (unidirectional stimulation), with the electrodes differing in surface area (Amassian et al., 1990, Stewart et al., 1990, Cracco et al., 1989, Amassian et al., 1989a, Amassian et al., 1989b). We have shown in nonhuman primates the capacity to produce focal frontal seizure induction under conditions when a unidirectional current flows from a small anterior anode (placed on the forehead over the nasion) to a large posterior cathode just anterior to the motor strip (Spellman et al., 2009). Furthermore, many of these seizures in primates did not result in motor convulsions. We tested this new stimulation method in 4 nonhuman primates, who on several occasions had seizure threshold titrated with current either flowing from the small anterior electrode to the large posterior electrode or the reverse (Spellman et al., 2009). In 7 of 7 tests, EEG seizures were evoked at low stimulus intensity and most did not result in motor convulsion. The seizure threshold in the instances of an electrographic seizure without motor convulsion was at the first step in the titration schedule, with only 3 mC being administered. For each animal, seizure threshold with typical ECT parameters is substantially higher. These findings were remarkable and demonstrated that this method can produce focal frontal seizures, which we have hypothesized as key to therapeutic mechanisms ([name] et al., 1983; [name], 1999, (Nobler et al., 1994, [name] et al., 1996). Furthermore, it appears that seizure threshold may be reduced with this approach ([name], 2004a).

We have recently completed preliminary open-label studies with FEAST, first at Columbia University, and then at the Medical University of South Carolina in Charleston (Nahas et al., 2013b). We have published the outcomes of the first 17 patients studied. One patient withdrew from the study after a single titration session. After the course of FEAST (median 10 sessions), there was a $46.1 \pm 35.5\%$ improvement in Hamilton Rating Scale for Depression (HRSD24) scores compared to baseline (33.1 ± 6.8 , 16.8 ± 10.9 ; $P < 0.0001$). Eight of 16 patients met response criteria ($\geq 50\%$ decrease in HRSD24) and 5/16 met remission criteria ($HRSD24 \leq 10$). Patients achieved full re-orientation (4 of 5 items correct) in 5.5 ± 6.4 min (median time = 3.6 min), timed from when their eyes first opened after treatment. We have now studied 18 more patients (see results below), and we are completing the study in the original IDE with another two more patients still to enroll.

This work allowed us to refine the treatment. For example, we selectively modified the electrode geometry to decrease interelectrode resistance. Additionally we

modified the titration schedule, now only administering a standard 800 ma ultrabrief pulse, and thus no longer titrating in the current domain.

II. Study Objectives

This study will provide preliminary evaluation of the following:

1. Further characterization of the efficacy of FEAST and the safety of the treatment.
 - a. The primary efficacy measure will be the 24-item Hamilton Rating Scale for Depression. The changes in these scores from before to immediately following the treatment course will be compared in patients treated with the FEAST methodology and matched to nonrandomized patients at our facilities who were treated with conventional ECT methods (ultrabrief right unilateral [RUL] ECT).
 - b. Acute and subacute cognitive side effects following FEAST will be assessed with a brief neuropsychological battery. The primary acute measures will be the time to return of orientation following seizure induction. The primary subacute measures will be assessment of retrograde amnesia for autobiographical information. The neuropsychological measures will be compared in the patients treated with the FEAST methodology (under this IDE) and matched (but nonrandomized) patients who are treated with conventional ECT methods (also covered under this IDE).
 - c. Safety will also be determined by examining the number and frequency of serious adverse events and adverse events.
2. Characterization of the focal nature of the seizure onset with FEAST and RUL ECT. We will use two main methods to address the issue of focality.
 - a. Resting state fMRI before and after a course of FEAST (or conventional RUL ECT). We will address whether FEAST causes changes in hyper connected prefrontal cortical subcortical networks, and whether such an effect is more restricted to prefrontal cortex with FEAST relative to conventional RUL ECT.
 - b. Peri-ictal EEG acquired immediately before, during and immediately after the FEAST seizure. We will acquire this in all patients at all treatment sessions. Again, for comparison, we will use identical EEG acquisition methods in patients treated with conventional RUL ECT.

Section IV.B.17 describes the statistical plan for addressing these objectives.

III. Report of Prior Investigations

A. Experience of the Investigators

The original applicant, [name], remains a key co-investigator on this proposal that is now transferred from NYSPI, Columbia University to the Institute of Psychiatry at MUSC. [name] been engaged since 1979 in research using ECT devices produced by the MECTA Corporation. The applicant has over 250 publications in the area of ECT and over 425 total publications. Representative efficacy and safety findings from the major studies over this period are reported in the following:

- [name] HA (2004): The convulsant and anticonvulsant properties of electroconvulsive therapy: towards a focal form of brain stimulation. *Clinical Neuroscience Review* 4:39-57.
- [name] HA, Prudic J, Devanand DP, Kiersky JE, Fitzsimons L, Moody BJ, McElhiney MC, Coleman EA, Settembrino JM (1993): Effects of stimulus intensity and electrode placement on the efficacy and cognitive effects of electroconvulsive therapy. *New England J Med* 328:839-46.

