The time to achieve full symptomatic improvement with antidepressant medications is typically estimated as 4 to 6 weeks (Quitkin et al., 1984, Quitkin et al., 1996). This delay until response may be longer in older patients (Salzman et al., 2002). In contrast, the average ECT course for major depression consists of 8-9 treatments ([name] et al., 1993; Prudic et al., 1996). Thus, when ECT is administered at a schedule of three treatments per week, the usual schedule in the US, full symptomatic improvement typically occurs more rapidly than with pharmacological treatment ([name] et al., 1995, Nobler et al., 1997b).

ECT is a highly structured treatment, involving a complex, repeatedly administered procedure that is accompanied by high expectations of therapeutic success, and involves an extensive consent process and period of patient education. Such conditions may augment placebo effects. Given this concern, a set of double-blind, random assignment trials were conducted in England during the late 1970's and 1980's that contrasted 'real' ECT with 'sham' ECT — the repeated administration of anesthesia alone. With one exception (Lambourn and Gill, 1978), real ECT was found consistently to be more efficacious than sham treatment (Freeman et al. 1978; Johnstone et al. 1980; West 1981; Brandon et al. 1984; Gregory et al. 1985; see [name] 1989 for a

[figure not shown]

Figure 1. Serial HRSD scores for groups treated with either low dosage (1 x ST) RUL or BL ECT in [name] et al. (1987a) [Study 1] and [name] et al. (1993b) [Study 2]. Note the strong replication of the effects.

review). Lambourn and Gill (1978) had used a form of real ECT, involving low stimulus intensity and right unilateral electrode placement, that is now known to be ineffective ([name] et al., 1987b, [name] et al., 1993, [name] et al., 2000b).

Overall, the real vs. sham ECT studies demonstrated that the passage of an electrical stimulus and/or the elicitation of a generalized seizure were necessary for ECT to exert antidepressant effects. Following the randomized acute treatment period, the patients who participated in these studies were free to receive other forms of acute or continuation treatment, including ECT. Consequently, information regarding the duration of symptomatic improvement with real versus sham treatment could not be obtained in this research.

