Across the sites 60 patients will be enrolled to achieve 40 FEAST patients who will fully complete this study at the MUSC Institute of Psychiatry, Brain Stimulation Service (BSS) in Charleston, SC, and at GRU in Augusta, GA and Aiken, SC. At both MUSC and GRU, roughly matched 30 patients (each) will also be recruited from those scheduled to receive UB RUL ECT to obtain a cohort of 40 RUL comparison patients. The FEAST and UB RUL ECT groups must meet identical inclusion/exclusion criteria and will undergo identical evaluation procedures. The only difference between the groups will be that one receives FEAST and other UB RUL ECT. The treatment received by the UB RUL ECT group will not be affected by participating in this protocol. This is an open label, non-randomized, non-masked study. Separate consent forms will be used in each group. We are thus asking FDA permission to study 60 patients with FEAST. An additional 60 patients will be studied who receive conventional ECT. Even though they are getting conventional ECT, they are covered by this FDA IDE as their data will be used for comparison purposes with FEAST.

Patients will be selected from those referred for ECT for the treatment of major depressive episode. To verify diagnosis, the SCID-P will be administered to derive DSM-V diagnosis (unipolar or bipolar major depressive episode) and relevant subtypes and specifiers (American Psychiatric Association, 2013).

Inclusion and exclusion criteria are presented in Table 2. Briefly, patients will be between the ages of 18 and 90 years and will provide informed consent. Exclusions include: history of schizophrenia, schizoaffective disorder or any non-mood disorder psychosis, rapid cycling bipolar disorder, central nervous system illness other than conditions associated with psychotropic exposure, alcohol or substance abuse or dependence in the past 3 months, pregnancy, epilepsy, inability to have stable medications, and ECT within the past six months.

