At MUSC, ECT sessions will be conducted in a dedicated ECT suite on the fifth floor of the Institute of Psychiatry. At GRU, ECT sessions can be either inpatient or outpatient, depending upon the patient's needs, and can occur either at Georgia Regents Medical Center in Augusta , Georgia, or at Aiken Regional Hospital in Aiken, South Carolina, depending upon patient preference. The custom device used for FEAST will not be used for any other purpose. [Patients receiving UB RUL ECT will be treated with a standard commercial MECTA Spectrum 5000Q. After the patient is medically stabilized following the administration of FEAST he/she will be moved by stretcher to an adjacent recovery room where she/he will complete neuropsychological testing (recovery of orientation, if not already obtained). Patients leave the recovery room only after being cleared by medical staff.

RUL ECT Stimulus Dosing. For the matched RUL sample, we will use the same MECTA device, but with conventional ECT settings. We will not use the FEAST electrodes, but instead will use conventional ECT electrodes. Seizure threshold will be determined at the first session, and subsequent treatments will be performed at 6 times seizure threshold. As this is a rough clinical comparison sample, all aspects of ECT treatment in these individuals will follow what is now routine clinical practice at MUSC and GRU. These details are outlined in the landmark paper regarding RUL ECT ([name] et al, 2008).

Number of Treatments. Duration of treatment will determined by a clinical evaluation team at each site. ECT is typically dynamically adapted to each person, attempting to deliver the necessary treatments for that patient, and no more. We incorporate that model in this IDE, similar to our algorithm in the first IDE. At MUSC that team is composed of [name], [name], and [name], Senior Nurse and ECT specialist. At GRU the ECT delivery team consists of Dr. [name] and [name], while depression severity, quality of life and cognitive ratings will be performed by [name], [name], MS, [name], MS or [name].

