FEAST and ultrabrief RUL ECT patients will be treated identically except as noted below. The traditional d'Elia electrode placement will be used for UB RUL ECT (American Psychiatric Association, 2001), with the frontotemporal electrode tangential to the midpoint of the line connecting the right auditory tragus and the canthus. The posterior electrode will be tangential to the vertex (midpoint of line connecting nasion and inion). Standard stainless steel 2" diameter electrodes will be used. If it is deemed that patients require a change in ECT modality, a switch to either brief pulse RUL or BL ECT will be implememnted, as clinically indicated.

B.8 Assessment of Efficacy

Clinician ratings. Instruments include the HRSD (24-item) (Hamilton, 1967), MADRS (Montgomery and Asberg, 1979), CGI (severity and improvement) (Guy, 1976), and the GAS (Endicott and Spitzer, 1978). A clinical evaluation team independently completes these scales on the basis of conjoint interviews, both at set time points (preECT baseline, 1-2 days after ECT termination) and the HRSD alone is also completed at spaced intervals (weekly during the ECT course). Interviews usually take place between 10 AM-12 PM to minimize variability due to diurnal variation.

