The primary aim of this study is to contrast FEAST and UB RUL ECT in these EEG measures of seizure onset and propagation. Specifically, we expect FEAST to show greater focality of seizure onset than UB RUL ECT, with seizure onset most manifest in the right frontal EEG with FEAST, and far greater activity in the left and right temporal leads with UB RUL ECT.

B.14 Quality Assurance and Data Management

A highly experienced rater will provide clinical ratings throughout the treatment period. Accuracy of the output of the FEAST device will be tested ([name] et al., 1994), and calibration signals regularly applied to the EEG recordings. The stimulus parameters used with the modified Spectrum 5000Q will both be recorded electronically and transferred to a database using the Spectrum's automatic EMR logging software. An experienced psychometrician will review all neurocognitive data. Data will be entered on digital forms using automatic flags for out-of-range and missing values. Any correction to a data record will be recorded in an audit notebook. The study database will be backed-up regularly.

B.15 Statistical Analyses

Data Screening. Data will be reviewed for extreme values. When distributional assumptions are not met, data will be transformed or nonparametric procedures used. Prior to statistical analyses, the study sites (MUSC vs. GRU) and treatment groups (FEAST vs. UB RUL ECT) will be compared in the baseline sociodemographic and clinical features, using ANOVA and log-linear analyses, with a liberal threshold to detect inequality ($P < 0.2$).

Hypothesis Testing. Even though this is a preliminary investigation, yielding effect sizes by which to power a subsequent randomized study, it is important to protect the Type I error rate by limiting primary analyses to a restricted and clearly specified set of hypotheses and outcome measures. The primary analyses will test the hypotheses stated below which address the objectives described in Section II. The major areas of investigation are effects on seizure threshold, electrophysiological (EEG) activity, efficacy, function, objective changes in cognition and subjective cognitive changes. The primary efficacy analyses will be conducted in the intent-to-treat sample.

Hypothesis 1. FEAST is substantially more efficient (i.e., lower ST) than traditional ECT, even when both use an ultrabrief (0.3 ms) pulse width.

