We do not anticipate that this form of ECT (unidirectional, ultrabrief pulse with spatial targeting) will have an adverse impact on efficacy, although this is not certain. Potential lack of efficacy likely constitutes the most significant risk of FEAST. Precautions have been taken in this protocol to mitigate this risk. First, patients who do show sufficient benefit after 5 treatments may receive a dosage increment, increasing the stimulus dose from 6xST to 9xST. In the community, dosing of UB RUL ST is often 8xST or more (e.g., (Loo et al., 2012)). Second, any patient who completes the research phase as a nonremitter will be offered a course of traditional ECT (UB RUL ECT, high dose RUL or BL ECT). Our preliminary experience in 35 patients clearly indicates that FEAST has potent antidepressant properties. We cannot, however, say with assurance that these properties are equivalent to traditional forms of ECT, without explicit comparison. This study provides important data in this respect, involving the first cotemporaneous comparison of FEAST and UB RUL ECT, albeit in a non-randomized and non-masked fashion. It is anticipated that the findings obtained here will provide the foundation for a subsequent RCT.

The protocol involves monitoring of objective and subjective side effects and includes provision for alternative treatment for patients who do not respond clinically. Although a large number of procedures are conducted, other than ECT, they are all noninvasive. Patients who consent to the protocol have the option of declining participation in specific procedures (e.g., fMRI studies), but can retain participation in the remaining procedures.

Finally, FEAST might present with two theoretical risks: superficial skin burn and intracerebral damage to excessive current density). The use of an electrode with small surface area could increase the impedance in the circuit and result potentially in skin burn or prevent the passage of the stimulus. This theoretical risk is minimized by the fact that the ECT device voltage limits and immediately aborts stimulus delivery when excessive impedance is encountered. In this protocol, we are requesting that the voltage/impedance

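### HRSD24 and CUAMI-SF are collected without masked rating or scoring, and the protocol does not settle who rates HRSD24 or whether that rater also steers treatment

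*Combined protocol and SAP*

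**What the plan says.** Section II, Objective 1a: "The primary efficacy measure will be the 24-item Hamilton Rating Scale for Depression". Objective 1b makes retrograde autobiographical amnesia the primary subacute cognitive measure and time to reorientation the primary acute one. Hypothesis 5 in IV.B.15 names orientation recovery time and CUAMI-SF as the two primary cognitive measures.

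Masking is ruled out in IV.B.1 ("This is an open label, non-randomized, non-masked study") and again in IV.C.2, where the comparison is described as made "albeit in a non-randomized and non-masked fashion".

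On who rates and who decides:
- IV.B.8, for HRSD, MADRS, CGI and GAS: "A clinical evaluation team independently completes these scales on the basis of conjoint interviews".
- IV.B.6, Number of Treatments: "Duration of treatment will determined by a clinical evaluation team at each site". III.D.2 lets a body of the same name recommend a higher stimulus dose after the fifth treatment.
- IV.B.6 gives one team for MUSC, including a senior nurse and ECT specialist, and no separate raters. For GRU it gives a delivery team and continues "while depression severity, quality of life and cognitive ratings will be performed by" a separate list of people.
- IV.B.14 speaks of one very experienced rater supplying clinical ratings throughout treatment. It adds: "An experienced psychometrician will review all neurocognitive data". Neither is said to be masked.
- IV.B.12 does not say who administers CUAMI-SF at MUSC.

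**The concern.** An interviewer who knows the treatment and expects a result can shift an interview-based score. The plan predicts no efficacy difference (Hypothesis 4) and a FEAST advantage in memory and reorientation (Hypothesis 5). One rating shift in FEAST's favour would help both predictions: it could cover an efficacy deficit and produce a memory benefit.

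The risk is greater if the HRSD24 rater also decides when to stop or whether to raise the dose. HRSD24 change governs stopping (IV.B.6). Percentage HRSD24 change is also a covariate for Hypotheses 2f and 6, and number of treatments is one for Hypothesis 5, so a shift would not stay within Hypothesis 4.

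IV.B.15 says the study is to yield effect sizes for powering a later randomized trial. A biased effect size would be carried into that design.

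**Working it through.** **Who rates.** The plan gives three descriptions of the HRSD24 rater. IV.B.8 has a clinical evaluation team. IV.B.6 uses the same name for the body that sets duration, and separates raters from deliverers only at GRU. IV.B.14 has a single rater. They cannot all be literally true at both sites. With names removed, overlap between raters and treaters at MUSC can be neither confirmed nor excluded. The shared name covers the clinician scales only, not CUAMI-SF. The time-blind videotape ratings mentioned in IV.B.8 belong to earlier studies.

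**Size.** The plan states no power, alpha, effect size or margin for either measure, so there is no figure to reproduce. What follows is an illustration.

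Inputs:
- 40 completers per group (IV.B.1).
- HRSD24 end-of-course SD 10.9 (pilot, Section I) or 11.2 (pilot, III.D.6).
- AMI-SF end-of-course SD 5.1 (pilot, III.D.6).
- Two-sided 5% test: assumed.
- Differential bias b: assumed.

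Formulas: SE = SD × √(2/40). With no true difference, P(reject) = 1 − Φ(1.96 − b/SE) + Φ(−1.96 − b/SE).

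HRSD24, SD 10.9: SE = 10.9 × √0.05 = 2.44.
- b = 1: b/SE = 0.41, P = 6.9%
- b = 2: b/SE = 0.82, P = 13.0%
- b = 3: b/SE = 1.23, P = 23.4%

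SD 11.2 gives SE 2.50 and 6.8%, 12.6% and 22.4%. Adjusting for baseline with an assumed correlation of 0.3 reduces the SD to 10.9 × √(1 − 0.09) = 10.4 and gives 7.1%, 13.8% and 25.2%. Adjustment sharpens the test and does not remove the bias.

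CUAMI-SF, SD 5.1: SE = 5.1 × √0.05 = 1.14. A bias of 0.5, 1 or 2 points gives 7.2%, 14.2% and 41.8%.

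**Concealment.** The HRSD24 difference detectable with 80% power is (1.96 + 0.84) × 2.44, about 6.8 points. A true 7-point difference has 82% power. An opposing 2-point bias leaves a net 5 points and 54% power. A true 3-point deficit would reach significance only 23% of the time even without bias, so for small deficits imprecision matters more than rater bias.

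**The case against.** The strongest reply is that the limitation is declared and the claims are scaled to it. III.D.2 calls the efficacy data preliminary, IV.B.5 makes the EEG comparison the primary goal with efficacy and side effects secondary, and a masked randomized trial is planned next. There are partial safeguards: a structured HRSD/MADRS interview with explicit anchors, independent ratings from conjoint interviews, and the self-report IDS-SR. These points stand and limit the severity. They do not answer the concern, because the study is still meant to supply effect sizes. The reasons given for abandoning blind randomization (limited data, doubtful equipoise) also do not bear on masking a rater. IDS-SR avoids rater expectation but not patient expectation.

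A reader might infer more than the documents support:
- That one MUSC team both treats and rates HRSD24 and CUAMI-SF. For HRSD24 this rests on a shared label that IV.B.14 contradicts. For CUAMI-SF nothing links the two.
- That the raters have a stake in FEAST. The manufacturer's section reports a patent but names no holder, and the GRU team is described only as experienced in ECT.
- That the remark "Such conditions may augment placebo effects" in III.B.1 concedes the point. It concerns expectation about ECT procedures, in the context of real-versus-sham trials. Here both groups receive active treatment.

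It is also fair to object that a masked end-of-course score should not be placed at the end of a weekly unmasked series. The Hypothesis 4 model would then confound time with a change of rater.

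**Conclusion.** The concern holds in a limited form. No masked rating or scoring is planned for HRSD24 or CUAMI-SF, and the sections on who rates HRSD24 must be reconciled. Orientation time is equally unmasked. It is assessed continuously after each seizure, so it is harder to mask.

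If a differential bias of 1 to 3 HRSD24 points existed, the nominal 5% error would be about 7% to 23%. This rests on an assumed bias, the pilot SD, 40 completers per group and a simple end-point contrast in place of the planned intent-to-treat repeated-measures model. The documents do not show that such a bias exists.

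A bias that differs by site is possible, given the different rating arrangements, but is not established. A site main effect would not remove it, and a site-by-group interaction could not distinguish it from a real difference. This is an inexpensive improvement worth making, not a defect that invalidates the study.

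**What to change.** 1. Reconcile IV.B.6, IV.B.8 and IV.B.14. State by role, for each site, who rates HRSD24, who administers CUAMI-SF, and whether either has a part in treatment decisions.
2. Have the planned psychometrician score and review CUAMI-SF, BSRT and mMMS from records carrying only the numeric code of IV.C.4, without treatment group.
3. Have the baseline and end-of-course HRSD24 and CUAMI-SF done by planned raters who are outside the treating team and are not told the group. At GRU these are the listed raters; at MUSC, use a planned rater wherever one is outside the treating team. Ask patients not to disclose their treatment, and record the rater's guess of group.
4. Keep the Hypothesis 4 repeated-measures model on the weekly ratings. Add, as a separate analysis, the baseline-adjusted end-of-course contrast from the masked rating, which matches Objective 1a. Report it beside the main model and IDS-SR.

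The cost is withholding labels from existing staff, some scheduling and one added analysis. In-course care is unchanged. Masking will be incomplete because some patients will disclose. At MUSC it is not assured without a further assessor, since the rater in IV.B.14 sees patients throughout treatment. Masked scoring cannot undo bias introduced in an unmasked interview, and none of this addresses non-random selection.
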